8.6.6. Pre-Discharge

Before the patient is discharged from the hospital the following steps are completed.

- [a] Record the patient's weight and vital signs at the pre-discharge visit on this page.
- [b] Obtain a blood sample for serum creatinine, blood urea nitrogen, hematocrit, and hemoglobin measurements.
- [c] Perform Ankle-Brachial Index testing bilaterally.
- [d] Perform a physical examination.
- [e] Other tests or imaging as needed.
- [f] Document any new or discontinued relevant medications (cardiac/circulatory).
- [g] A copy of the hospital discharge report or note is requested.
- [h] Report any adverse finding from the diagnostic testing, or specific events that occurred since the procedure. If an event is a serious adverse event, provide the additional event details on the **Serious Adverse Event** section of the CRF. See §8.7 for adverse event reporting requirements
- [i] The hospital staff should complete the *Patient Implant Card* (provided in the bifurcated stent graft product packaging) and give it to the patient so that he or she can carry it at all times. The patient should be instructed to refer to the card anytime he or she visits a health practitioner, particularly for any additional diagnostic procedures (e.g., MRI).

8.6.7. Post-Discharge Follow-up Visits

The patient post-discharge follow-up visits occur at **30±14 days** (one month visit), **180±30 days** (six month visit), **365±60 days** (one year visit), **730±90 days** (two year visit), **1095±90 days** (three year visit), **1460±90 days** (four year visit), and **1825±90 days** (five year visit).

- [a] Obtain a blood sample for serum creatinine, blood urea nitrogen, hematocrit, and hemoglobin measurements.
- [b] Perform a physical exam.
- [c] Perform Ankle-Brachial Index testing bilaterally.
- [d] Diagnostic Imaging:
 - **CT Scan:** When a CT Scan is performed, collect it as a high resolution, contrast-enhanced CT scan using the same acquisition parameters required by the Core Lab as for the baseline exam. Forward the CT Scan to the Core Lab identified in §2.2. A copy of the diagnostic report is requested.
 - As per institutional standard of care, record any other imaging performed and attach a copy of the diagnostic report[s].
- [e] Document any new or discontinued relevant medications (cardiac/circulatory).
- [f] Report any adverse finding from the diagnostic testing, or events that occurred since hospital discharge. If an event is a serious adverse event, provide the additional event details on the **Serious Adverse Event** section of the CRF. See §8.7 for adverse event reporting requirements.

8.7. ADVERSE EVENT REPORTING

Throughout the course of the study, all adverse events will be recorded on the applicable **ADVERSE EVENT** CRF and in the patient's medical records. The seriousness, date of onset, date of resolution, severity, action taken, relationship to the device, and relationship to the procedure will be identified by the Investigator.

8.7.1. General Definitions

An adverse event (AE) is any undesirable clinical occurrence in a patient administered a product and that does not necessarily have a causal relationship with the treatment. An AE can therefore be any unintended sign, symptom or disease temporally associated with the use of an investigational product, whether or not related to the use of the product.

A serious adverse event (SAE) is an AE that results in death, is life threatening, requires in-patient hospitalization or that prolongs hospitalization, results in persistent or significant disability/incapacity, or that is a congenital anomaly or birth defect.

An unanticipated adverse event (UAE) is any serious adverse effect on health or safety or any life threatening problem or death caused by or associated with a device, if that effect, problem, or death was not previously identified in nature, severity, or degree of incidence. Additionally, an unanticipated adverse event includes any other unanticipated serious problem associated with a device that relates to the rights, safety, or welfare of subjects.

Severity of an AE is a clinical determination of the event intensity. The severity assessment for a clinical AE should be completed using the following definitions as guidelines:

Mild (+1): Awareness of sign or symptom, but easily tolerated.

Moderate (+2): Discomfort enough to cause interference with usual activity.

Severe (+3): Incapacitating with inability to work or do usual activity.

NOTE: An event that is fatal should be recorded as death on the **ADVERSE EVENT** CRF. The cause of death will be detailed on the **Serious Adverse Events** section of the form.

Relationship to device or procedure of an AE is a judgment determination made by the Investigator that there is a logical connection between device use (e.g., delivery system manipulation) and the occurrence of the AE.

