8.7.2. Reporting of Device or Procedure Related Events

For all patients, Investigators shall submit to Endologix and to the reviewing EC or IRB a report of any adverse device-related or procedure-related event, including, but not limited to, hospitalization or death within 10 working days after the Investigator first learns of the event. Each of these events will be investigated by Endologix. If it is determined that a UAE has occurred and presents an unreasonable risk to subjects, all investigations or parts of investigations presenting that risk will be terminated. Termination of the investigation will occur within five (5) working days after notice of the effect is received at Endologix. The terminated investigation will not be resumed without the approval of the EC.

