8.7.3. Reporting of SAEs

Any SAE occurring during the study period must be recorded on the appropriate **ADVERSE EVENT** CRF and **Serious Adverse Events** section of the CRF.

For any SAE, fax the ADVERSE EVENT CRF within 24 hours of awareness to the Endologix Clinical department at [contact]. All patients with an SAE must be followed and outcomes reported. The Investigator should supply to Endologix and the responsible EC/IRB with a complete, written case history (AE forms) and any additional requested information (e.g., other diagnostic testing, discharge reports, autopsy reports, etc.).

Deaths

For any patient death, regardless of cause or timing, an autopsy should be requested. If the family has agreed to the conduct of an autopsy, the autopsy report is to be attached to the **ADVERSE EVENT** CRF where the death is reported.

A device explant kit will be provided to the hospital for processing and shipment to an independent pathologist per established methods. To request a kit, send a fax to Endologix at [contact], or contact Endologix by telephone at [contact].

In all cases, the death certificate is to be attached to the **ADVERSE EVENT** CRF where the

death is reported. Every attempt should be made to obtain as much detailed information on the events or conditions leading up to the death as possible. If the patient was hospitalized, a copy of the discharge summary source document is required.

Secondary Interventions

For patients that experience any non-diagnostic invasive secondary treatment of the groin access areas or of the abdominal aortoiliac vessels (e.g., hematoma drainage, vascular exploration for bleeding, iliac stenting, thrombectomy, additional device placement for endoleak, embolization for Type II endoleak, etc.), it is important to identify the area, region or vessel segment that is involved and the specific procedure performed on the relevant **ADVERSE EVENT CRF**. A copy of the discharge summary source document is required.

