8.7.4. Anticipated Adverse Events

Adverse events that could potentially occur during this investigation are called anticipated adverse events and are listed in alphabetical order:

- Access site complications and sequelae (e.g., dehiscence, infection, pain, hematoma, pseudoaneurysm)
- Allergic reaction to contrast agent (e.g., pruritus, urticaria, bronchospasm, angioedema, hypotension or anaphylaxis that occurs during or post-procedure)
- Amputation
- Anesthetic complications and sequelae (e.g., aspiration)
- Aneurysm enlargement
- Aneurysm rupture
- Arterial damage or trauma (e.g., bleeding, perforation, dissection, rupture)
- Arterial or venous thrombosis and/or pseudoaneurysm
- Arteriovenous fistula
- Bleeding requiring transfusion and/or surgical intervention
- Bowel complications (e.g., ileus, ischemia, infarction, necrosis)
- Cardiac complications and sequelae (e.g., arrhythmia, myocardial infarction, congestive heart failure, hypotension, hypertension)
- Catheter fragmentation and sequelae (e.g., embolization, vessel trauma)
- Claudication
- Coagulopathy
- Death (due to any cause)
- Edema
- Embolization (micro and macro) with transient or permanent ischemia or infarction
- Endoleak
- Fever and localized inflammation

- Genitourinary complications and sequelae (e.g., ischemia, fistula, incontinence, hematuria, impotence, infection)
- Hepatic failure
- Infection of the aneurysm, device access site, including abscess formation, transient fever and pain.
- Local or systemic neurologic complications and sequelae, transient or permanent (e.g., stroke, transient ischemic attack, paraplegia, paraparesis, paralysis, numbness and/or tingling in legs)
- Lymphatic complications and sequelae (e.g., lymph fistula)
- Thrombosis or occlusion of stent graft or arterial vessel of the lower extremities
- Pulmonary/respiratory complications and sequelae (e.g., pneumonia, respiratory failure, prolonged intubation, pulmonary embolism)
- Renal complications and sequelae (e.g., artery occlusion, infarction, insufficiency, failure)
- Secondary procedure
- Stent graft: improper component placement; incomplete component deployment; component migration; suture break; occlusion/thrombosis; infection; stent fracture; graft material wear; dilatation; erosion; puncture and perigraft flow
- Surgical conversion to open repair

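### Device and procedure relatedness are rated separately but share one device-use test, so harm from the procedure alone can miss the related-event report and, if serious, CEC adjudication

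*Combined protocol and SAP*

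**What the plan says.** §8.7 requires two attributions for every event: "relationship to the device, and relationship to the procedure will be identified by the Investigator". §8.7.1 then treats them together. It opens with "Relationship to device or procedure of an AE is a judgment determination made by the Investigator", and the judgment to be made is that "there is a logical connection between device use (e.g., delivery system manipulation) and the occurrence of the AE". The procedure is named in the subject of that sentence but not in the test. No other part of the supplied text gives investigators a test for relationship to the procedure.

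The rating has two uses:

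- §8.7.2 requires the investigator to send the sponsor and the EC/IRB "a report of any adverse device-related or procedure-related event" within 10 working days, and commits the sponsor to investigate each one.
- §8.7.7 excludes from CEC assessment any event that is non-serious or is reported as clearly unrelated. The same section bases the event analyses on the CEC's categorization, and §6.1 makes the CEC the body that determines the MAE composite.

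Other provisions do not depend on the rating. §8.7 says "Throughout the course of the study, all adverse events will be recorded on the applicable" form. For any serious event, §8.7.3 has the site fax the adverse "EVENT CRF within 24 hours of awareness to the Endologix Clinical department", and expects a written case history to go to both the sponsor and the EC/IRB.

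**The concern.** Some harm comes from the operation and not from the device: aspiration under anesthesia, a reaction to contrast, a bleed from anticoagulation. The protocol expects such harm. §8.7.4 lists "Anesthetic complications and sequelae (e.g., aspiration" among its examples), and also lists contrast reactions, bleeding and coagulopathy. §8.6.5 has the site time the end of anesthesia and heparin reversal as steps of the procedure. Yet an investigator who applies the §8.7.1 test as written has no basis for calling such an event procedure-related.

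Two things are at stake. The first is consistency: with up to 15 sites, some investigators will follow the subject of the sentence (device or procedure) and others its test (device use), so the procedure rating will not mean the same thing everywhere. The second is routing: the rating decides whether an event enters the dated related-event report, and it can decide whether a serious event is adjudicated for the primary safety endpoint.

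**Working it through.** The documents state no figure that depends on relatedness, so there is nothing to reproduce or recompute. The check is to set the provisions side by side and follow one kind of event through them: a complication of anesthesia, contrast or heparin with no device involvement.

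1. **Rating.** §8.7 has two fields; §8.7.1 has one test, device use. Taken literally, both fields ask the same question, and this event can be answered unrelated in each.

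2. **Non-serious event, rated unrelated.** It stays on the adverse event form (§8.7; also §8.6.5[e] and §8.6.6[h] for events around the procedure and before discharge). It stays in the results, because §6.3 reports serious and non-serious events without a relatedness filter. It loses the §8.7.2 report and the sponsor investigation. The CEC exclusion adds nothing here, because §8.7.7 leaves non-serious events unassessed under any rating.

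3. **Serious event, rated unrelated.** It is recorded and counted as in step 2. It also reaches the sponsor within a day and the EC/IRB by case history (§8.7.3), whatever the rating. It loses the §8.7.2 report and investigation. That is a real loss, because §8.7.3 sets no deadline for the EC/IRB and no duty on the sponsor to investigate. §8.7.5 does not fill the gap for complications listed in §8.7.4, since it covers unanticipated device effects only.

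4. **Serious event, reported as clearly unrelated.** In addition to step 3, §8.7.7 takes it out of CEC assessment. The MAE definition in §6.1 and §8.7.7 has no relatedness condition, and several components could arise without device involvement: pneumonia or respiratory failure with prolonged ventilation, a sustained creatinine rise counted as renal failure, or myocardial infarction. Such an event meets the endpoint definition but may not be put before the body that determines the endpoint. Under §10.1(g) and (h) the DSMB reviews adjudicated safety data, so the event could be absent there too.

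5. **Deaths.** §8.7.7 says details of all deaths go to the CEC, so they are probably assessed. The exclusion sentence is not expressly waived for them.

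6. **What counts as clearly unrelated.** The supplied text does not say whether this means unrelated to the device, to the procedure or to both, nor whether an ordinary unrelated rating under §8.7.1 is enough. The weaker the §8.7.1 test is for the procedure, the more this matters.

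**The case against.** The strongest reply is that the sentence is loosely drafted but harmless. Attribution is a judgment, delivery-system manipulation is only an example, the sentence names the procedure, and §8.7.4 lists anesthetic and contrast complications as events of this investigation. A sensible investigator can mark an intra-operative aspiration procedure-related. The case report forms and their completion guide, where field instructions would normally sit, are not in the supplied text. The CEC also classifies the events it reviews, where possible, as related to the aneurysm procedure or to access site closure, and §10.1(g) describes its remit without the exclusion.

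Much of this stands. It shows that misrating is possible, not certain. It does not supply a procedure test. The CEC's classification applies only to events it assesses, and draws a different line from device versus procedure. The general remit in §10.1(g) does not cancel the explicit exclusion in §8.7.7.

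A reader might infer several stronger things that the documents do not support:

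- **That these events drop out of the results.** All adverse events are recorded and reported whatever the rating. No supplied section defines a result based on the investigator's relatedness rating. The Statistical Analysis Plan appears only as the title of Attachment 5, so a related-event table can be neither confirmed nor ruled out.
- **That serious procedural harm goes unreported.** §8.7.3 carries it to the sponsor and the EC/IRB regardless of relatedness.
- **That each re-rated patient moves a related-event rate by 2 percentage points.** That is 1/50, the weight of one patient at maximum enrollment, applied to a rate the documents never define.
- **That the two ratings can never differ.** That follows only if every investigator applies the test literally.
- **That late implant failure is lost.** Device use can reasonably include an implanted device, and the core laboratory assesses stent fracture and graft failure at follow-up irrespective of relatedness (§6.3).

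**Conclusion.** The point holds as a defect in a stated rule. §8.7 and §8.7.2 treat device and procedure relatedness as two things, and §8.7.1 tests only one. A complication of the procedure alone can therefore be rated unrelated on both, with two consequences: loss of the 10-working-day report and sponsor investigation, and, for a serious event reported as clearly unrelated, loss of CEC adjudication, on which the primary MAE endpoint depends.

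No numerical size can be computed. The documents give neither the frequency of such events nor the share that would be misrated. The conclusion assumes that at least some investigators apply §8.7.1 literally, that the forms and completion guide not supplied here do not already separate the two definitions, and, for the endpoint consequence, that the §8.7.7 exclusion is applied as written. The change should be made because it is cheap and the second consequence touches the primary endpoint; the documents do not show that the endpoint is in fact biased.

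**What to change.** Replace the relatedness sentence in §8.7.1 with two definitions, rated separately on the adverse event form:

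- **Device-related:** a reasonable link to the fenestrated extension, the renal or bifurcated stent graft, or their delivery systems, at any time, including late implant failure.
- **Procedure-related:** a reasonable link to any part of the index procedure or a secondary procedure, including anesthesia, access, contrast and anticoagulation, whether or not a device was involved.

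Add to §8.7.7 that every potential MAE goes to the CEC whatever relatedness rating the investigator gave. The definitions alone reduce the number of events wrongly reported as unrelated but leave the exclusion in place; this sentence removes it for the events that matter to the primary endpoint.

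The cost is a few sentences in the protocol and a matching change to the form completion guide. Events already rated under the present sentence would need re-rating to be comparable. More events will be reported as procedure-related, and somewhat more will go to the CEC. The change concerns classification and reporting only.

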8.7.2. Reporting of Device or Procedure Related Events

For all patients, Investigators shall submit to Endologix and to the reviewing EC or IRB a report of any adverse device-related or procedure-related event, including, but not limited to, hospitalization or death within 10 working days after the Investigator first learns of the event. Each of these events will be investigated by Endologix. If it is determined that a UAE has occurred and presents an unreasonable risk to subjects, all investigations or parts of investigations presenting that risk will be terminated. Termination of the investigation will occur within five (5) working days after notice of the effect is received at Endologix. The terminated investigation will not be resumed without the approval of the EC.

8.7.3. Reporting of SAEs

Any SAE occurring during the study period must be recorded on the appropriate **ADVERSE EVENT** CRF and **Serious Adverse Events** section of the CRF.

For any SAE, fax the ADVERSE EVENT CRF within 24 hours of awareness to the Endologix Clinical department at [contact]. All patients with an SAE must be followed and outcomes reported. The Investigator should supply to Endologix and the responsible EC/IRB with a complete, written case history (AE forms) and any additional requested information (e.g., other diagnostic testing, discharge reports, autopsy reports, etc.).

Deaths

For any patient death, regardless of cause or timing, an autopsy should be requested. If the family has agreed to the conduct of an autopsy, the autopsy report is to be attached to the **ADVERSE EVENT** CRF where the death is reported.

A device explant kit will be provided to the hospital for processing and shipment to an independent pathologist per established methods. To request a kit, send a fax to Endologix at [contact], or contact Endologix by telephone at [contact].

In all cases, the death certificate is to be attached to the **ADVERSE EVENT** CRF where the

death is reported. Every attempt should be made to obtain as much detailed information on the events or conditions leading up to the death as possible. If the patient was hospitalized, a copy of the discharge summary source document is required.

Secondary Interventions

For patients that experience any non-diagnostic invasive secondary treatment of the groin access areas or of the abdominal aortoiliac vessels (e.g., hematoma drainage, vascular exploration for bleeding, iliac stenting, thrombectomy, additional device placement for endoleak, embolization for Type II endoleak, etc.), it is important to identify the area, region or vessel segment that is involved and the specific procedure performed on the relevant **ADVERSE EVENT CRF**. A copy of the discharge summary source document is required.

8.7.4. Anticipated Adverse Events

Adverse events that could potentially occur during this investigation are called anticipated adverse events and are listed in alphabetical order:

- Access site complications and sequelae (e.g., dehiscence, infection, pain, hematoma, pseudoaneurysm)
- Allergic reaction to contrast agent (e.g., pruritus, urticaria, bronchospasm, angioedema, hypotension or anaphylaxis that occurs during or post-procedure)
- Amputation
- Anesthetic complications and sequelae (e.g., aspiration)
- Aneurysm enlargement
- Aneurysm rupture
- Arterial damage or trauma (e.g., bleeding, perforation, dissection, rupture)
- Arterial or venous thrombosis and/or pseudoaneurysm
- Arteriovenous fistula
- Bleeding requiring transfusion and/or surgical intervention
- Bowel complications (e.g., ileus, ischemia, infarction, necrosis)
- Cardiac complications and sequelae (e.g., arrhythmia, myocardial infarction, congestive heart failure, hypotension, hypertension)
- Catheter fragmentation and sequelae (e.g., embolization, vessel trauma)
- Claudication
- Coagulopathy
- Death (due to any cause)
- Edema
- Embolization (micro and macro) with transient or permanent ischemia or infarction
- Endoleak
- Fever and localized inflammation

- Genitourinary complications and sequelae (e.g., ischemia, fistula, incontinence, hematuria, impotence, infection)
- Hepatic failure
- Infection of the aneurysm, device access site, including abscess formation, transient fever and pain.
- Local or systemic neurologic complications and sequelae, transient or permanent (e.g., stroke, transient ischemic attack, paraplegia, paraparesis, paralysis, numbness and/or tingling in legs)
- Lymphatic complications and sequelae (e.g., lymph fistula)
- Thrombosis or occlusion of stent graft or arterial vessel of the lower extremities
- Pulmonary/respiratory complications and sequelae (e.g., pneumonia, respiratory failure, prolonged intubation, pulmonary embolism)
- Renal complications and sequelae (e.g., artery occlusion, infarction, insufficiency, failure)
- Secondary procedure
- Stent graft: improper component placement; incomplete component deployment; component migration; suture break; occlusion/thrombosis; infection; stent fracture; graft material wear; dilatation; erosion; puncture and perigraft flow
- Surgical conversion to open repair

